4.3. Handling Withdrawals and Missing Data

Unless specified otherwise in this section, for all variables, only observed data will be used in the statistical analyses; i.e., there is no plan to estimate missing data.

All binary response and remission variables will be imputed as non-response if any of the following cases occur:

- Participants discontinuing treatment and/or trial during the 14-week treatment period regardless of the reason
- Participants who used rescue medications for UC or CD prior to their week 14 evaluation of remission/response (see [Section 4.5](#) for classification rules)
- Participants undergoing major UC or CD related surgery (see [Section 4.6](#) for classification rules)

4.3.1. Missing Week 14 Endoscopy Assessment

All binary response and remission variables that are based on the week 14 endoscopy will be imputed as non-responder/non-remission if the week 14 endoscopy assessment is not available for the participant. In particular,

- UC participants who did not complete evaluation for clinical remission at week 14 will be reported as non-remitters.
- CD participants who did not complete evaluation for endoscopic response at week 14 will be reported as non-responders.

4.3.2. Missing items – MMS, CDAI, PRO2-UC, and PRO2-CD

The MMS, CDAI, PRO2-UC and PRO2-CD are composite scores (see derivation rules in [Appendix 4](#), [Appendix 5](#)). The patient-reported items of stool frequency (UC and CD), rectal bleeding (UC), and abdominal pain (CD) are based on e-diary data collected in a 7-day window before the assessment date of the score, which may be extended to 10 days prior to the assessment date, as described in [Appendix 4](#). A minimum of 3 consecutive days of completed diary entries or 4 nonconsecutive days are necessary for each parameter, otherwise the corresponding item will be considered missing.

If any item of a composite score is missing, then the score will be considered missing.

If a score is missing, then the participant will be considered a non-responder /non-remitter for all binary outcomes based on this score, except for intermittent missing data visits that will be excluded from that visit analyses.

4.3.3. Missing Items – Robarts Histopathology Index

If any of the 4 subscores are missing, then the final score is set to missing. If the final score is missing, then the participant's response will be imputed as a non-remitter for week 14.

4.3.4. Missing Items – Geboes Index

If any of the items are missing, then the score is set to missing. If the score is missing, then the participant's response will be imputed as a non-remitter for week 14.

4.3.5. Missing Items – Global Histologic Activity Score

If any of the 8 items are missing, then the total score is set to missing. If the total score is missing, then the participant's response will be imputed as a non-responder for week 14.

4.4. Trial Days and Visits

For by-visit summaries, if there are multiple assessments at a postbaseline visit then the last non-missing assessment at that visit will be used for the summary (this includes scheduled and unscheduled assessments).

Trial days are numbered relative to the first day of trial drug administration. The start of treatment (Day 1) is defined as the date on which a participant takes the first dose of trial drug, as recorded on the clinical database. Days will be numbered relative to treatment start (i.e., ..., -2, -

1, 1, 2, ...; with day 1 being the first day of trial drug administration and day –1 being the day before the first day of trial drug administration).

4.5. Classification of Intercurrent Events – Initiation or Dose Increase of Inflammatory Bowel Disease Medications

The intercurrent events of initiation or dose increase medications used to treat the IBD will be classified as follows:

Medication	ICE Classification
5-ASA; sulfasalazine (SSZ)	Important protocol deviations, including use or changes in other medications (treatment policy)
Immunosuppressants – other than MTX	Important protocol deviations, including use or changes in other medications (treatment policy)
Immunosuppressants – MTX	Rescue medication
Systemic corticosteroids (IV, PO, IM, suppository)	Rescue medication
Advanced IBD therapies (biologics, JAK inhibitors, S1P inhibitors)	Rescue medication

As described in the primary estimand (Section 1.2), ICEs classified as “Rescue medication” will be handled using the composite strategy, i.e., the participant will be reported as non-remitter/non-responder; ICEs classified as “Important protocol deviations, including use or changes in other medications” will be handled using the treatment policy, i.e., data after the ICE will be used regardless of the ICE. These strategies will be applied to all response/remission efficacy endpoints.

All participants with initiation or dose increase of IBD medications will be reviewed in the statistical data review meeting prior to DBL, where the classification will be confirmed on a case-by-case basis.

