8.4. Clinical Laboratory Tests

Laboratory test results will be presented in standard international (SI) units.

Summary statistics for chemistry, hematology, and urinalysis laboratory tests will be presented at baseline and each visit that this is measured. Laboratory values and changes from baseline to each visit will be summarized using descriptive statistics. Listings of all individual participants' laboratory tests will be presented.

Shifts (below, within, and above the normal range) from baseline to each visit that this is measured will be summarized using participant counts.

Summaries of potentially clinically significant abnormal values will include all postbaseline values (including scheduled, unscheduled, and early termination visits). The incidence of potentially clinically significant abnormal values will be summarized for laboratory variables using descriptive statistics with the criteria specified in [Table 6](#).

Table 6: Criteria for Potentially Clinically Significant Laboratory Values

Test Category	Test	Criterion value
Serum chemistry	ALT	$>5 \times \text{ULN}$ $>5 \times \text{BL}$ if BL is abnormal ($> \text{ULN}$)
	AST	$>5 \times \text{ULN}$ $>5 \times \text{BL}$ if BL is abnormal ($> \text{ULN}$)
	ALP	$>5 \times \text{ULN}$ $>5 \times \text{BL}$ if BL is abnormal ($> \text{ULN}$)
	Creatinine	$>3 \times \text{ULN}$ $>3 \times \text{BL}$ if BL is abnormal ($> \text{ULN}$)
	Bilirubin (total)	$>3 \times \text{ULN}$ $>3 \times \text{BL}$ if BL is abnormal
	Potassium	$<3.0 \text{ mmol/L}$ $>6.0 \text{ mmol/L}$
	Sodium	$<120 \text{ mmol/L}$ $>155 \text{ mmol/L}$
	Calcium	Corrected serum calcium of $>12.5 \text{ mg/dL}$ Corrected serum calcium of $<7.0 \text{ mg/dL}$
	Phosphate	$<1.4 \text{ mg/dL}$
Hematology	Hemoglobin	$<8.0 \text{ g/dL}$ and/or decrease of 3.0 g/dL from BL $> \text{ULN} + 4.0 \text{ g/dL}$
	WBC counts	$<2.0 \times 10^9/\text{L}$ $>100 \times 10^9/\text{L}$
	Neutrophil	$<0.5 \times 10^9/\text{L}$
	Lymphocyte	$<0.5 \times 10^9/\text{L}$
	Platelet counts	$<50 \times 10^9/\text{L}$
Urinalysis	HGB	≥ 2 unit increase from BL
	Glucose	≥ 2 unit increase from BL
	Ketones	≥ 2 unit increase from BL
	Total protein	≥ 2 unit increase from BL

ALP=alkaline phosphatase; ALT=alanine aminotransferase; ANC=absolute neutrophil count AST=aspartate aminotransferase; BL = baseline; BUN=blood urea nitrogen; GGT=gamma-glutamyl transpeptidase; HGB=hemoglobin; LDH=lactate dehydrogenase; ULN=upper limit of normal range; WBC=white blood cell.

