8.4.1. Liver-Related Laboratory Tests

Maximum post-baseline elevation in ALT, AST and bilirubin will be summarized as incidence and shift tables using the criteria specified in [Table 7](#).

Table 7: Liver-Related Laboratory Tests Criteria

Test	Criterion Value
ALT	>3 x ULN
	>5 x ULN
	>10 x ULN
	>20 x ULN
AST	>3 x ULN
	>5 x ULN
	>10 x ULN
	>20 x ULN
ALT or AST	>3 x ULN
	>5 x ULN
	>10 x ULN
	>20 x ULN
Bilirubin (total)	≥2 x ULN
Hy's Law	{ALT ≥3 x ULN or AST ≥3 x ULN} and {bilirubin (total) ≥2 x ULN} and {ALP <2 x ULN}

Incidence of participants meeting laboratory criteria for Hy's Law, i.e.

{ALT ≥3 x ULN or AST ≥3 x ULN} and {bilirubin (total) ≥2 x ULN} and {ALP <2 x ULN}, will be listed.

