Shifts (normal, abnormal not clinically significant, and abnormal clinically significant) from baseline to each visit that this is measured, and from baseline to overall (anytime) will be summarized using participant counts for the investigator interpretation. For overall result interpretation the worst postbaseline finding for the participant (the abnormal finding if there are both normal and abnormal findings) will be used in the summaries.

Summary statistics for ECG variables will be presented at baseline and each visit that it is measured. Actual values and changes from baseline to each visit will be summarized using descriptive statistics.

The incidence of potentially clinically significant abnormal values will be summarized using descriptive statistics with the criteria specified in [Table 10](#). Note that to qualify as potentially clinically significant abnormal, a value needs to meet both criteria below, if applicable: e.g., have a value beyond the criterion value and a change of at least the magnitude specified in the change relative to baseline column. A listing of potentially clinically significant ECG results will be presented.

Table 10: Criteria for Potentially Clinically Significant Abnormal ECG

ECG Test	Criterion Value	Change Relative to Baseline
PR Interval	≥200 msec	Increase of at least 25% from baseline
QRS Duration	≥110 msec	Increase of at least 25% from baseline
QTcF Interval	≥450 msec and <500 – male or ≥460 msec and <500 – female	≥30 and <60 msec increase from baseline
	≥450 msec and <500 – male or ≥460 msec and <500 – female	≥60 msec increase from baseline
	≥500 msec	≥30 and < 60 msec increase from baseline
	≥500 msec	≥60 msec increase from baseline

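### The general laboratory shift table is by visit only and keeps the last value, so a normal same-visit repeat hides an abnormal result short of the Table 6 and Table 7 criteria

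*SAP*

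**What the plan says.** SAP section 4.4 sets the rule for several assessments at one post-baseline visit: "the last non-missing assessment at that visit will be used for the summary (this includes scheduled and unscheduled assessments"). It gives no window for deciding which visit an unscheduled test belongs to.

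Section 8.4 defines the general laboratory shift as follows: "Shifts (below, within, and above the normal range) from baseline to each visit that this is measured will be summarized using participant counts". It makes no exception to section 4.4 and adds no any-time or worst-value shift. Section 1.1 lists change from baseline in laboratory results among the safety measures.

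Other outputs do not depend on the last value:

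- Potentially clinically significant values (section 8.4, Table 6): "Summaries of potentially clinically significant abnormal values will include all postbaseline values (including scheduled, unscheduled, and early termination visits").
- Liver tests (section 8.4.1, Table 7): "Maximum post-baseline elevation in ALT, AST and bilirubin will be summarized as incidence and shift tables using the criteria specified in" Table 7.
- ECG interpretation (section 8.6), for the shift to any time after baseline: "For overall result interpretation the worst postbaseline finding for the participant (the abnormal finding if there are both normal and abnormal findings) will be used".
- Listings (section 8.4): "Listings of all individual participants' laboratory tests will be presented".

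**The concern.** A laboratory test is often repeated because the scheduled result was abnormal. If the repeat is normal and is filed at the same visit, section 4.4 keeps the repeat and drops the result that prompted it. Normal scheduled results are less likely to be repeated, so the replacement is selective and runs mainly toward the within-range category. Part of the return to normal is regression to the mean.

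At stake is whether the shift table shows mild to moderate laboratory abnormalities. If the drug pushes an analyte past its limit, more participants are open to replacement on active treatment than on placebo, and the absolute difference between arms shrinks.

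**Working it through.** **Step 1: follow single results through the planned tables.** Assume a scheduled abnormal value and a normal repeat at the same visit. Criteria are from Tables 6 and 7.

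| Scheduled value | By-visit shift | Table 7 (maximum) | Table 6 (all values) |
|---|---|---|---|
| ALT 2.5 x ULN | within | no (needs >3) | no (needs >5) |
| ALT 4 x ULN | within | yes | no |
| ALT 6 x ULN | within | yes | yes |
| Creatinine 2 x ULN | within | not covered | no (needs >3) |
| Neutrophils 0.9 x 10^9/L | within | not covered | no (needs <0.5) |

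The first, fourth and fifth rows would be visible only in listings. Some directions also have no Table 6 criterion: phosphate and platelets have only a low limit. A high value in either relies wholly on the by-visit shift.

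**Step 2: size.** The SAP states no figure to reproduce and gives no repeat rate, so this is an illustration on assumed inputs:

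- first and repeat values are bivariate normal with correlation 0.7;
- the upper limit lies at 1.96 SD, and the drug shifts the mean by 0.5 SD (placebo 0);
- a share q of abnormal values is repeated within the visit, and normal values are not repeated.

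Let p be the share whose scheduled value is above the limit, and L the probability that the repeat is at or below the limit given that the first value was above it. The share counted as high is p x (1 - q x L).

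- Placebo: p = 2.50%, L = 0.669.
- Active: p = 7.21%, L = 0.570.
- Difference on scheduled values: 7.21 - 2.50 = 4.71 points.

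| q | Placebo | Active | Difference |
|---|---|---|---|
| 10% | 2.50 x (1 - 0.067) = 2.33% | 7.21 x (1 - 0.057) = 6.80% | 4.47 |
| 50% | 2.50 x (1 - 0.335) = 1.66% | 7.21 x (1 - 0.285) = 5.16% | 3.50 |
| 100% | 2.50 x 0.331 = 0.83% | 7.21 x 0.430 = 3.10% | 2.27 |

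**Step 3: range over the correlation.** At correlation 0.5, L is 0.815 (placebo) and 0.717 (active). At 0.9, L is 0.407 and 0.337. The same formula then gives a difference of 4.4 to 4.6 points for q = 10%, 3.1 to 4.0 for q = 50%, and 1.6 to 3.3 for q = 100%.

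**Step 4: in participants.** With the planned 40 per arm and indication (section 2.5) and correlation 0.7, the loss in the difference is (4.71 - 4.47)% x 40 = 0.1 participant at q = 10%, (4.71 - 3.50)% x 40 = 0.5 at 50%, and (4.71 - 2.27)% x 40 = 1.0 at 100%.

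**The case against.** A reader might infer that laboratory, vital-sign and ECG shifts are all undercounted and that safety signals will be lost. The SAP does not support that.

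- Marked abnormalities are counted from all post-baseline values. The ALT, AST and bilirubin tables use the maximum, from >3 x ULN (ALT, AST) or >=2 x ULN (bilirubin), and a repeat cannot lower a maximum.
- ECG interpretation already has a worst-finding shift, and vital signs have no shift table.
- Not every Table 6 criterion is extreme. A haemoglobin fall of 3.0 g/dL from baseline and a rise of two units in a urinalysis test also count.
- The SAP does not say that only abnormal results are repeated. A repeat prompted by symptoms could replace a normal value with an abnormal one. A repeat filed at a different visit replaces nothing.
- The shift table is descriptive. The stopping rules and the Bayesian safety comparisons (sections 8.3 and 13.1) use adverse event types.
- The attenuation is on the absolute scale. In the illustration with all values repeated, the ratio of shares rises, from 7.21/2.50 = 2.9 to 3.10/0.83 = 3.7.
- A last-value rule has a rationale: it lets a repeat correct a spurious result.

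All of this stands, and it narrows the point considerably. It does not cover analytes outside Table 7 whose abnormal value misses Table 6, or liver tests between the normal limit and the Table 7 thresholds. Listings show those values but do not count them by arm.

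**Conclusion.** The point holds in a limited form and is minor. Sections 4.4 and 8.4 together let a normal same-visit repeat remove an abnormal result from the general laboratory shift table and from the by-visit changes from baseline, and the error runs mainly toward undercounting. For abnormal values that meet no Table 6 or Table 7 criterion, no other summary table picks the result up.

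The size is not known from the SAP. With 10% of abnormal values repeated within the visit, the illustrated loss is about 0.2 of 4.7 points. It reaches about half of the difference only if every abnormal value is repeated. These figures rest on the assumed normal model, limit, correlation and drug shift, and on the premise that repeats follow abnormal results. They should not be read as an estimate of what will happen in this trial.

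**What to change.** In section 8.4, add a shift from baseline to the worst post-baseline value, lowest and highest, for all laboratory tests, using scheduled and unscheduled results. This follows the approach of section 8.6 for ECG interpretation and closes the gap in the shift counts whichever value the by-visit tables use.

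Preferably, also state in section 4.4 that by-visit laboratory summaries use the scheduled value and take an unscheduled one only when the scheduled value is missing. This second change is more debatable, because spurious scheduled results that a repeat would have corrected then stay in the by-visit tables. Such results would also enter the worst-value shift.

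The cost is one more table and a few lines of SAP text. No new data are needed.

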4.6. Classification of Intercurrent Events – Inflammatory Bowel Disease Related Surgery

All IBD-related Major surgery will be considered as a major UC/CD related surgery that will be handled using composite strategy. Classification of surgeries will be done on a case-by-case basis and reviewed in the blinded statistical data review meeting prior to DBL.

As described in the primary estimand (Section 1.2), ICEs classified as “Major UC/CD related surgery” will be handled using the composite strategy, i.e., the participant will be reported as non-remitter/non-responder. This strategy will be applied to all response/remission efficacy endpoints.

Note that participants undergoing IBD surgery will likely require perioperative systemic corticosteroids and thus will be treated using the composite strategy, i.e., these participants will be reported as non-remitters/non-responders, on that basis.

5. TRIAL POPULATION

5.1. General

The ITT analysis set will be used for all trial population summaries. Summaries will be presented by treatment group, pooled TEV-48574, and all participants, separately by indication (UC or CD) and pooled (UC and CD).

5.2. Participant Disposition

Participants screened, participants screened but not randomized, will be summarized only for the total group (all participants) using participant counts.

Participants in the ITT, mITT, safety, and immunogenicity analysis set, participants who complete the 14-week treatment period, and participants who complete the trial and rollover into the LTE trial or complete the trial via the follow-up period will be summarized using descriptive statistics. The denominator for calculating the percentages will be the number of participants in the ITT analysis set.

Participants who withdraw from the trial prior to completion of the 14-week treatment period and participants who withdraw from the trial during the follow-up period after completing the treatment period, if applicable, will also be summarized using descriptive statistics by reason for withdrawal.

5.3. Demographics and Baseline Characteristics

The continuous variables of participant age, weight, height, and body mass index (BMI), and will be summarized using descriptive statistics. The categorical variables of participant sex, race, ethnicity, BMI category (18.5<; \geq 18.5 and <25; \geq 25 and <30; \geq 30), smoking status (current or former smoker yes/no), previous exposure to advanced therapy for IBD (yes/no), and region (North America/Eastern EU - Poland/Eastern EU – Other/Western EU/Japan/Israel) will be summarized using descriptive statistics for each category. Missing categories will be presented if necessary.

In addition, a summary of participants by region and country will be provided by indication and overall.

5.4. Disease Characteristics

The following disease characteristics variables at baseline will be summarized using descriptive statistics: time since initial IBD diagnosis (years), MMS and components (UC), PRO2-UC score (UC), SES-CD (CD), CDAI score, and stool frequency and abdominal pain components (CD), PR02-CD (CD), fecal calprotectin value, hsCRP value, and albumin value.

5.5. Baseline IBD Treatments

The incidence of baseline concomitant IBD therapies will be summarized using descriptive statistics using the following categories:

- Glucocorticosteroids
- 5-ASA
- Immunosuppressants

UC and CD treatment categories definitions will be reviewed in the blinded data review meeting prior to DBL, and additional categories/medications may be added.

In addition, baseline use of corticosteroids and dose will be summarized using descriptive statistics for equivalent prednisone dose, as follows:

- Descriptive statistics of the dose (min, max, mean, etc.)
- Incidence of current treatment with oral corticosteroids (Yes/No), and a breakdown to dose categories:
 - <10mg
 - 10-20mg
 - >20mg
 - Budesonide
 - 3mg to < 6 mg
 - 6 mg to \leq 9 mg
 - > 9 mg

The conversion table of oral corticosteroid doses to equivalent prednisone dose is provided in [Appendix 6](#).

5.6. Medical History

All medical history will be coded using the Medical Dictionary for Regulatory Activities (MedDRA). The incidence of medical history abnormalities will be summarized using descriptive statistics by system organ class (SOC) and preferred term (PT). Participants are counted only once in each SOC category, and only once in each PT category.

5.7. Inflammatory Bowel Disease History

The continuous variable of number of hospitalizations due to UC or CD will be summarized using descriptive statistics. The categorical variables of histology findings to support the diagnosis of UC/CD (yes/no), colonic stricture (yes/no), and history of colonic or small bowel obstruction (yes/no) will be summarized using descriptive statistics for each category. Missing categories will be presented if necessary.

5.8. Prior Therapy and Medication

Any prior therapy, medication, or procedure for IBD (anytime in the past) will be recorded in the case report form (CRF). Any other prior therapy, medication, or procedure a participant has had within 4 weeks prior to the screening visit will be recorded in the CRF. Generic or trade name,

indication, and dosage will be recorded. The sponsor will encode all therapy and medication according to the World Health Organization (WHO) drug dictionary (WHO Drug).

Prior therapies and medications will include all medications taken and therapies administered before the first day of trial drug administration.

The incidence of prior therapies and medications will be summarized using descriptive statistics by therapeutic class and PT. Participants are counted only once in each therapeutic class category, and only once in each PT category.

In addition, the incidence of prior therapies, medications, or procedures for IBD will be summarized using descriptive statistics using the following categories:

- Glucocorticosteroids
- 5-ASA
- Immunosuppressants
- TNF inhibitors
- Integrin inhibitors
- IL-12/23 inhibitors
- Anti-IL-23
- JAK inhibitors
- S1P Modulators
- Investigational drugs

UC and CD treatment categories will be reviewed in the blinded data review meeting prior to DBL, and additional categories/medications may be added. Investigational drugs will be classified on a case-by-case basis.

The number of advanced therapies for IBD that a participant was exposed to in the past will be summarized using descriptive statistics.

